5.3.1 Study Product Compliance and Exposure

Treatment compliance will be assessed daily during the 12-week treatment period – the end of the treatment period will be defined as the completion of the last virtual visit 4 MFI questionnaire. If the virtual visit 4 MFI questionnaire is not completed, the date used as the definition will be the treatment initiation date plus 84 days. Both definitions have an acceptable window of +/- 5 days. Compliance will be analyzed descriptively by reporting the absolute and relative frequency of subjects with 80% compliance to treatment per block of 4 treatment weeks and overall, for each group. A compliance score will be calculated for each subject by dividing the number of days the allocated treatment was taken by the number of days the treatment was allocated. The compliance score will be summarized for each group and compared between groups.

Additional information on number of doses taken, number of missed doses, number of expected doses, and dose compliance will be presented both in Table 14.2.1.1 and Listing 16.2.5.1 where:

- Number of doses taken is defined as:
 - Overall: Number of times daily diary indicates a dose was taken between treatment initiation and Week 12 MFI completion date. If the virtual visit 4 MFI questionnaire is not completed, the date used as the definition will be the treatment initiation date plus 84 days.
 - Treatment Start to Week 4: Number of times daily diary indicates a dose was taken between treatment initiation and Week 4 MFI completion date. If the virtual visit 2 MFI questionnaire is not completed, the date used as the definition will be the treatment initiation date plus 28 days.
 - Week 4 to Week 8: Number of times daily diary indicates a dose was taken between Week 4 MFI completion date and Week 8 MFI completion date. If the

Haleon Confidential

CCI Statistical Analysis Plan template v7.0

- virtual visit 3 MFI questionnaire is not completed, the date used as the definition will be the treatment initiation date plus 56 days.
- Week 8 to Week 12: Number of times daily diary indicates a dose was taken between Week 8 MFI completion date and Week 12 MFI completion date. If the virtual visit 4 MFI questionnaire is not completed, the date used as the definition will be the treatment initiation date plus 84 days.
-
- Number of expected doses is defined as:
 - Overall: Week 12 MFI Completion Date - Treatment Start Date.
 - Treatment Start to Week 4: Week 4 MFI Completion Date - Treatment Start Date.
 - Week 4 to Week 8: Week 8 MFI Completion Date – Week 4 MFI Completion Date.
 - Week 8 to Week 12: Week 12 MFI Completion Date – Week 8 MFI Completion Date.
- Number of missed doses is defined as number of expected doses – number of actual doses taken for each time period.
- Dose compliance (%) = $[100 \times (\text{Number of doses taken} / \text{Expected number of dose})]$.

Compliance will be tabulated using absolute and relative frequencies, and compliance score using mean, standard deviation, minimum and maximum values and median (see Table 14.2.1.1 and Listing 16.2.5.1).

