5.1.3 Analysis Populations

Three analysis populations are defined.

Population	Definition / Criteria	Analyses Evaluated
Safety	
 • Comprise of all subjects who receive at least one dose of study product. • This population will be based on the treatment the subject actually received. 	
 • Safety
Modified Intent-To-Treat (mITT)	
 • Comprise of all randomized subjects with completed baseline visit (visit 1), at least one completed post-baseline MFI domain assessment, and taken at least one dose of allocated product. • This population will be based on the treatment to which the subject was randomized. 	
 • Demographics • Baseline Characteristics • Efficacy • Subgroup analyses

Population	Definition / Criteria	Analyses Evaluated
	
 Any subject who receives a randomization number will be considered to have been randomized. 	
Per-Protocol (PP)	
 Comprised of all subjects in the mITT population who have adhered to treatment regime and were not affected by protocol deviations. 	
 Sensitivity (Primary endpoint)

Note: Please refer to [Appendix 1](#): List of Data Displays which details the population to be used for each display being generated.

The numbers of subjects included in each of the analysis populations will be summarized (Table 14.1.1). Subjects excluded from any of the analysis populations will be listed in Listing 16.2.3.1, with the reason for exclusion.

The primary population for assessment of efficacy will be the mITT Population. A PP analysis will be performed for efficacy analysis of the primary endpoint if at least 10% of the mITT subjects are excluded from the PP Population. Efficacy data determined to have been potentially impacted by a protocol deviation will be excluded from the PP analysis. A decision on whether a protocol deviation impacts efficacy data and whether to perform a PP analysis will be made at the BDRM.

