5.4.2 Handling of Missing Values

MMRM analyses account for missing data using ‘a missing at random’ assumption, i.e., there is a systematic relationship between the propensity for missing values and the observed data, but not the missing data. Under such assumptions, MMRM is shown to provide unbiased estimates of the treatment effect whilst analysis of only complete cases using analysis of covariance (ANCOVA) is biased (Ashbeck and Bell 2016; Baron et al. 2008).

Such complete case analysis requires a ‘missing completely at random’ assumption to remain unbiased and this is unlikely to hold, i.e., the fact that the data are missing is independent of the observed and unobserved data.

Using an MMRM, it will therefore be assumed that a subject with missing data at one post-baseline assessment visit would have obtained a similar efficacy result at that visit compared to a subject using the same investigational product with similar non-missing results at other timepoints (baseline and the other post-baseline assessment visits).

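### Does a missing Week 4 or Week 8 MFI date leave block compliance in SAP 5.3.1 without a denominator?

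*SAP*

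**What the plan says.** SAP section 5.3.1, repeated in the new version in Appendix 2, derives four quantities overall and for each block: doses taken, expected doses, missed doses and dose compliance.

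- **Doses taken** is a diary count. Overall it is "Number of times daily diary indicates a dose was taken between treatment initiation and Week 12 MFI completion date", and each block has its own version. If a block-end MFI is missing, a substitute is given. For Week 8 the condition and its date read "virtual visit 3 MFI questionnaire is not completed, the date used as the definition will be the treatment initiation date plus 56 days". The corresponding dates are start plus 28 days for Week 4 and start plus 84 for Week 12. The Week 12 rule also stands in the opening paragraph as part of the definition of the end of treatment.
- **Expected doses** is a difference of two dates. The later blocks read "Week 4 to Week 8: Week 8 MFI Completion Date – Week 4 MFI Completion Date" and "Week 8 to Week 12: Week 12 MFI Completion Date – Week 8 MFI Completion Date". No substitute date is repeated here.
- **Missed doses** links the two: "Number of missed doses is defined as number of expected doses – number of actual doses taken for each time period".
- Separately, a **compliance score** is obtained by "dividing the number of days the allocated treatment was taken by the number of days the treatment was allocated", and subjects are classed at 80% per block and overall.

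Missing intermediate MFIs are foreseen. The mITT population in section 5.1.3 asks only for "at least one completed post-baseline MFI domain assessment", and section 5.4.2 discusses "a subject with missing data at one post-baseline assessment visit".

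**The concern.** A percentage needs its numerator and denominator over the same days. Here the numerator has a rule for a missing Week 4 or Week 8 MFI and the denominator has none. A missing Week 8 MFI removes the end of block 2 and the start of block 3, so two of three blocks lose their stated expected doses, missed doses and percentage. One programmer might leave those cells blank while another fills them with the substitute dates.

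Two smaller points add to this. The section does not say whether *between* two dates includes both of them, and it does not say whether days allocated in the compliance score means the same as expected doses. If any of this mattered, it would show in Table 14.2.1.1 and Listing 16.2.5.1, and possibly in what is seen at the blinded data review meeting.

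**Working it through.** No figure in the plan needs reproducing, because 5.3.1 gives definitions only. The check is date arithmetic on those definitions.

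**Inputs.** Treatment starts on Day 1 and visits fall on Days 28, 56 and 84, each with +5 days (SAP Table 1). The substitute dates are start + 28, + 56 and + 84, which are Days 29, 57 and 85. Expected doses = end date − start date. The other MFIs are taken as completed on the nominal days.

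**1. All MFIs present.** 28 − 1 = 27, 56 − 28 = 28 and 84 − 56 = 28. The sum is 83 = 84 − 1. Each denominator is a single fixed subtraction.

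**2. One intermediate MFI missing, substitute date carried into expected doses.**

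| Missing | Block 1 | Block 2 | Block 3 | Sum | Overall |
|---|---|---|---|---|---|
| Week 8 (boundary Day 57) | 28 − 1 = 27 | 57 − 28 = 29 | 84 − 57 = 27 | 83 | 84 − 1 = 83 |
| Week 4 (boundary Day 29) | 29 − 1 = 28 | 56 − 29 = 27 | 84 − 56 = 28 | 83 | 84 − 1 = 83 |

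The sum always agrees with the overall count, since (b1 − start) + (b2 − b1) + (end − b2) = end − start. Overall compliance therefore never depends on a Week 4 or Week 8 date.

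**3. Could another denominator be meant?** Assume the Week 4 MFI on Day 33, the Week 8 MFI missing, and 20 doses recorded up to the substitute date, Day 57.

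- Substitute date in both counts: 57 − 33 = 24 expected, 20/24 = 83.3%, 4 missed.
- A nominal 28: 20/28 = 71.4%, 8 missed, although the diary was counted over only 24 days.
- Next available MFI (Day 84): 84 − 33 = 51, 20/51 = 39.2%, 31 missed, of which 51 − 24 = 27 lie after the diary count stopped.

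The 80% class does change between these. Only the first uses one period for both terms, which is what defining missed doses as expected minus taken for each period requires.

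**4. End dates.** With full adherence, counting one end date gives 27/27, 28/28, 28/28 and 83/83, all 100%. Counting both gives 28/27 = 103.7%, 29/28 = 103.6% twice, 84/83 = 101.2% overall, and 83 − 84 = −1 missed doses. The denominator is the same either way; only the diary count moves. The second convention produces impossible values for every fully adherent subject, so it would be seen at the first run.

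**5. Two ratios.** If days allocated is taken as Days 1 to 84, a subject with 67 doses, none on Day 84, and the Week 12 MFI exactly on Day 84 scores 67/84 = 79.8% against dose compliance of 67/83 = 80.7%. With the MFI one day later, expected doses are 85 − 1 = 84 and both ratios are 67/84. The disagreement needs that exact combination.

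**6. Frequency.** The documents give no rate of missed intermediate MFIs. For 240 completers there are 240 × 3 = 720 blocks, and each such subject affects two. At assumed rates of 0%, 5% and 10% (0, 12 and 24 subjects) this is 0, 24 and 48 blocks: 0%, 3.3% and 6.7%.

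**The case for a change.** The strongest case is that the sponsor rewrote this definition during blind data review precisely to settle its dates, and the rewrite is still incomplete. A rule supplied only in code is not pre-specified, and step 3 shows that the choice can move a subject across 80%. The frequency range is also confined to completers. Up to 20% of 300, or 60 subjects, may drop out; those who leave before Week 8 lack the same stated denominators and appear in the listing of all randomized subjects. Per-protocol membership requires adherence to the regimen, and section 5.1.2 lists compliance among the possible important deviations, so these figures may be looked at when exclusions are decided.

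The literal gap stands. So does the silence on end dates, although section 5.1.1 does add one day when it defines time in the study.

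The consequence does not stand. The missing rule is not open to free choice: the dates are printed a few lines above, under the same block names, and the alternatives contradict the missed-dose definition. For subjects who drop out, Appendix 2 states the aim of keeping a 12-week measurement period, which the same dates serve. Missed questionnaires are also limited among subjects who attend, since Protocol section 5.7 provides reminders, staff contact and completion during the visit. Per-protocol exclusions are blinded, case-by-case decisions with no 80% rule.

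Section 6 of the SAP still describes the virtual-visit date as the fallback for Week 12. That section is a summary of changes, and Appendix 2 records the replacement, so the operative text is not in doubt.

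**Conclusion.** This is a gap in wording that analysts fill sensibly from the section itself, and it calls for no change to the plan. The start + 28 and start + 56 dates serve as block end and as the next block's start in both counts, with one end date counted so that the diary total matches the subtraction. On that reading every fully adherent subject scores 100% and the blocks add up to the overall figure.

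The effect is confined to block-level cells in one descriptive table and one listing: 0% to 6.7% of completers' blocks if 0% to 10% of completers miss one intermediate MFI. Those rates are assumptions, and dropouts would add an unknown number. The rule is the same in both arms. The primary MMRM, the multiplicity procedure and the study's success criterion do not use compliance. The conclusion rests on 80% remaining a descriptive class, as the SAP has it, and not a per-protocol cut-off.

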5.3.2 Prior and Concomitant Medication

Prior medications/non-drug therapies and concomitant medications/significant non-drug therapies used prior to treatment initiation and in the treatment phase will be listed (Listing 16.2.4.3)

Prior medications/treatments, including prescription and non-prescription drugs, dietary supplements and herbal remedies, taken in the last 30 days and prior to signing the informed consent form, will be documented in the CRF. The prior and concomitant medications will be coded using a validated medication dictionary, CCI.

Prior medications and prior non-drug treatments will be listed by subject, with drug name, CCI Drug Synonym, reason for medication, route, dose, frequency, start date, start day relative to the study product start date, end date and end day relative to the study product start date (Listing 16.2.4.3) for all safety subjects. Prior medications are defined as those which stopped before the first use of the study product.

Haleon Confidential

CCI Statistical Analysis Plan template v7.0

Concomitant medications and concomitant non-drug therapies taken during treatment will be listed similarly (Listing 16.2.4.4) for all safety subjects with either ongoing or end date displayed. Concomitant medications are defined as medications that started or stopped on or after the first use of the study product or are ongoing.

Unknown dates will not be imputed. However, if the start or stop date is unknown, then it will be assumed to be concomitant medication, unless the partial start date or stop date indicates differently.

5.4 Analysis of Efficacy

5.4.1 Primary Efficacy Endpoint

5.4.1.1 Primary Efficacy Endpoint Definition

The primary efficacy variable are the MFI domain scores:

- *General Fatigue*: Items 1, 5, 12, 16
- *Physical Fatigue*: Items 2, 8, 14, 20
- *Reduced Activity*: Items 3, 6, 10, 17
- *Reduced Motivation*: Items 4, 9, 15, 18
- *Mental Fatigue*: Items 7, 11, 13, 19

Items are answered on a 5-point scale and recoded so that higher scores represent higher levels of fatigue.

Change from Baseline will be calculated at the subject level by subtracting the baseline score from scores assessed at 4, 8 and 12 weeks. The baseline score will be the screening (Day -7 to Day -2) MFI scores.

5.4.1.2 Statistical Hypothesis, Model, and Method of Analysis

The primary analyses assess the following hypothesis for each MFI domain score:

$$H_0: MFI_{12w-baseline_{Control}} = MFI_{12w-baseline_{Intervention}}$$

$$H_1: MFI_{12w-baseline_{Control}} \neq MFI_{12w-baseline_{Intervention}}$$

Where $MFI_{12w-baseline_{Control}}$ represents the change in MFI domain scores from baseline to 12 weeks in the control group, and $MFI_{12w-baseline_{Intervention}}$ refers to the change in the intervention group.

Change from baseline for each of the MFI domains listed above will be analyzed using a linear mixed-effects model for repeated measures (MMRM) with randomized treatment arm, timepoint as a factor and [treatment x timepoint] interaction as fixed effects, and the respective baseline MFI domain score as a covariate. Subject will be included as a repeated measure with an unstructured covariance matrix. Kenward-Rogers degrees of freedom will be applied (Kenward and Roger 1997). The difference between the least square mean change from baseline for the treatment compared to placebo group at Week 12 from the MMRM will be presented along with the two-sided p-value and 95% confidence interval (CI).

Using the above model, the adjusted mean change from baseline in MFI domains will also be reported by study product along with the 95% confidence intervals (CIs) and p-values testing for a non-zero change from baseline.

A significance level of 5% is used to evaluate the primary endpoint. To account for multiple comparisons, a Bonferroni-Holm correction will be applied to the p-values and CIs of the mean change between groups for the MFI domain scores at week 12. Change from Baseline in each of the MFI domain scores at earlier timepoints will only be assessed for confirmatory evidence if the change from the later timepoint achieves a statistically significant difference. Each domain will only be evaluated if the change from Baseline to 12 weeks (primary endpoint) was significant at the Bonferroni-Holm adjusted significance level. A significance level of 5% applies to all subsequent analyses of timepoints. This strategy will begin at Week 12, then move to Week 8, then to Week 4. There will be no further adjustments for multiplicity for other secondary endpoints. Both adjusted and non-adjusted p-values will be reported (where applicable).

The assumption of normality and homogeneity of variance in the MMRM will be investigated. In case of violation of these assumptions, a suitable non-parametric test (such as: Van Elteren Test) will be performed to assess the change from Baseline comparison. The results will be provided to support the MMRM results.

For each MFI domain listed above, the value at each timepoint (baseline, week 4, week 8 and week 12) and the corresponding change from baseline will be summarized descriptively for each treatment group. Raw means (+/- standard errors, SE) for each MFI endpoint at each assessment timepoint will be plotted by treatment group.

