8.3 Statistical Analyses

Additional details of the proposed statistical analysis will be documented in the statistical analysis plan (SAP), which will be written following finalization of the protocol and prior to study unblinding/analysis (as appropriate). This section is a summary of the planned statistical analyses of the primary and key secondary endpoints and a brief summary of how other collected data will be analyzed.

The mITT population will be used for all efficacy analyses.

All p-values presented will be two-sided and assessed at the 5% significance level. A sequential testing strategy will be used to adjust for the comparisons between the Emergen-C and placebo group at each assessment time point.

Change from Baseline in each of the MFI domain scores at earlier timepoints will only be assessed for confirmatory evidence if the change from the later timepoint achieves a statistically significant difference. Each domain will only be evaluated if the change from Baseline to 12 weeks (primary endpoint) was significant at the Bonferroni-Holm adjusted significance level. A significance level of 5% applies to all subsequent analyses of timepoints. This strategy will begin at Week 12, then move to Week 8, then to Week 4. There will be no further adjustments for multiplicity for other secondary endpoints.

Summary Statistics (mean, median, SE, SD, minimum, maximum) will be presented for each outcome variable at each assessment time point. Raw means (+/- SE) of the primary and secondary endpoints will be plotted by treatment group.

The results from each Mixed Model with Repeated Measures (MMRM) will be tabulated, presenting the least square mean change from baseline for each treatment group at each timepoint and the comparison between Emergen-C and Placebo, with two-sided p-values and 95% CIs.

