8.3.2 Secondary Endpoint Analysis(es)

The secondary endpoints of each MFI domain at Week 4 and Week 8 will be analyzed as described for the primary endpoint. Non-adjusted p-values and 95%-CIs will be reported, which need to be interpreted in light of the results of the primary endpoint, as described in section 8.2.

Similarly, the secondary endpoint for each of the individual MFI questions will be analyzed as described for the primary endpoint, but with baseline of the MFI domain score replaced with the individual MFI question score at baseline for the respective MFI item for each timepoint (Week 4, Week 8 and Week 12).

The secondary endpoint for the each of the supplementary QoL questions will also be analyzed using the same MMRM model described above, but with baseline of the MFI domain score replaced with the Baseline of the respective QoL question for each timepoint (Week 4, Week 8 and Week 12).

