5.5 Analysis of Secondary Objectives

5.5.1 Efficacy (Secondary)

The secondary endpoints of each MFI domain at week 4 and week 8 will be summarized descriptively and analyzed as described for the primary endpoint. Non-adjusted *p*-values and 95%-CIs will be reported, which need to be interpreted in light of the results of the primary endpoint.

Similarly, the secondary endpoint for each of the individual MFI questions will be summarized descriptively and analyzed as described for the primary endpoint, but with baseline of the MFI domain score replaced with the individual MFI question score at baseline for the respective MFI item for each timepoint (week 4, week 8 and week 12).

The secondary endpoint for each of the supplementary quality of life (QoL) questions will also be summarized descriptively and analyzed using the same MMRM model described above, but with baseline of the MFI domain score replaced with the baseline of the respective quality of life question for each timepoint (week 4, week 8 and week 12).

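### Week 8 and Week 4 MFI domain results are called confirmatory at an unsplit 5% per domain, although error across the five domains is controlled only at Week 12

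*SAP*

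**What the plan says.** Protocol 8.3 introduces the multiplicity approach with "A sequential testing strategy will be used to adjust for the comparisons between the Emergen-C and placebo group at each assessment time point". Protocol 8.3 and SAP 5.4.1.2 then give the same rule. Holm covers the five domains at Week 12. Domain scores "at earlier timepoints will only be assessed for confirmatory evidence if the change from the later timepoint achieves a statistically significant difference". The SAP adds "Each domain will only be evaluated if the change from Baseline to 12 weeks (primary endpoint) was significant" at the Holm-adjusted level, and the protocol says the same. The order is Week 12, Week 8, Week 4. The level for the later steps is given by "A significance level of 5% applies to all subsequent analyses of timepoints", and the paragraph goes on: "There will be no further adjustments for multiplicity for other secondary endpoints".

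The secondary-endpoint sections are brief. Protocol 8.3.2 says "The secondary endpoints of each MFI domain at Week 4 and Week 8 will be analyzed as described for the primary endpoint", with non-adjusted p-values and 95% CIs, "which need to be interpreted in light of the results of the primary endpoint, as described in section 8.2". SAP 5.5.1 says that "each MFI domain at week 4 and week 8 will be summarized descriptively and analyzed as described for the primary endpoint", also with non-adjusted results to be read in light of the primary endpoint.

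Protocol 2 defines success by any one domain at Week 12. SAP Appendix 1 marks the domain MMRM table over time (Table 14.2.2.1.2) for topline.

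**The concern.** Within one domain, testing Week 12, then 8, then 4, each at the same level and each only after the one before is significant, is a valid fixed sequence. The plan has five such sequences. Holm shares 5% among them at Week 12, but from Week 8 on each surviving domain receives the full 5%. Neither document divides the level across domains at Week 8 or Week 4, yet both treat these results as confirmatory, and the protocol describes the strategy as an adjustment at each time point.

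The gap opens when at least one domain has a real Week 12 effect and some earlier comparison in a domain that passes is truly null. A claim of early onset in some domain could then be reported as confirmatory without control across domains. Weeks 4 and 8 are secondary endpoints, so what is at stake is the status of an early-onset claim and not the success of the trial.

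Two smaller points concern wording. The phrase that a domain is evaluated only if Week 12 was significant leaves open whether a domain that fails is analysed at all at Weeks 4 and 8. Protocol 8.3.2 also sends the reader to Section 8.2 for the interpretation rule. Section 8.2 defines analysis populations and data exclusions; the rule is in 8.3.

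**Working it through.** **Inputs from the documents.** Five domains; two-sided 5%; Holm at Week 12; 5% per test afterwards (Protocol 8.3, SAP 5.4.1.2). 120 evaluable per group, 0.5 SD, 1% level for sample size (Protocol 4.1).

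**Assumed.** The documents give no correlations. Between-domain correlation is taken from 0 to 0.9 and across-visit correlation from 0 to 0.6. Subscales of one questionnaire are more plausibly at 0.7–0.9.

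**The plan's own figure.** The per-domain level is 0.05/5 = 0.01. The noncentrality is 0.5 × √(120/2) = 3.873. Power is Φ(3.873 − 2.576) = 0.903, which reproduces the stated figure of over 90%. The exact t calculation gives 0.898, a difference that does not matter here.

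**Limits by hand, independent domains.**
- If k domains pass Week 12 and none differs at Week 8, the chance of a false Week 8 result is 1 − 0.95^k: 5.0%, 9.75%, 14.3%, 18.5% and 22.6% for k = 1 to 5. Whatever the correlation, it cannot exceed 5 × 5% = 25%.
- If one domain works strongly at Week 12 and every other hypothesis is null, Holm tests the other four from 0.05/4, so their Week 12 error is 1 − 0.9875^4 = 4.9%. Adding a 5% test at Week 8 in the effective domain gives 1 − 0.9875^4 × 0.95 = 9.7%.

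**Simulation.** Correlated z-statistics for five domains at three visits, noncentrality 3.873 where effective (0.3 × √60 = 2.324 for the smaller effect), with the plan's rule applied as written; 300,000 replicates per scenario. An error is any rejection of a true null at Week 12, 8 or 4. Separately coded runs of 200,000 replicates agree within about 0.3 points.

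| True pattern | Any false rejection, all correlations | Between-domain 0.7–0.9 |
|---|---|---|
| Five domains, Week 12 only | 8.4–21.9% | 8.4–14.2% |
| Three domains, Week 12 only | 8.5–17.1% | 8.5–13.2% |
| Two domains, Week 12 only | 7.2–13.2% | 7.2–10.9% |
| One domain, Week 12 only | 5.6–9.1% | 5.6–7.8% |
| Five domains, Weeks 12 and 8, not Week 4 | 7.9–21.4% | 7.9–14.0% |
| Three domains at all visits, two at Week 12 only | 5.6–9.4% | 5.6–7.9% |
| Five domains, 0.3 SD, Week 12 only | 5.1–11.6% | 5.1–7.7% |
| No effect anywhere | 2.3–4.9% | within the same range |
| All domains, all visits | 0% | 0% |

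A single effective domain's own Week 12, 8, 4 sequence stays at or below 4.9%, which confirms that the excess arises across domains and not within one.

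**The case against.** The strongest case against the point is that it changes little. Success rests on Week 12 alone, where control is intact. Weeks 4 and 8 are secondary, and both documents say that their p-values are non-adjusted. The topline flag is on a single table that also carries the primary result, so it does not show that early results would be presented as confirmatory. All of this stands, and it keeps the point minor. It does not remove the word confirmatory from Protocol 8.3 and SAP 5.4.1.2.

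The upper figures also come from a corner: five uncorrelated subscales, uncorrelated visits, a 0.5 SD effect in all domains at Week 12 and exactly none at Week 8. With between-domain correlation 0.7–0.9 and across-visit correlation 0.6, the five-domain figure is about 8.4–12.6%. The studies tabulated in Protocol 1.1 include differences at about four weeks, so a late-only effect is not the expected pattern. A reader might infer that the trial runs a 22% error rate; the documents do not support that.

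A reader might also infer that the gate contradicts the secondary-endpoint sections. It need not. The gate follows directly on the sentence about confirmatory evidence and can be read as governing only that status, while Protocol 8.3.2 and SAP 5.5.1 report non-adjusted estimates to be read in light of Week 12. Only a loose phrase and a wrong section number remain.

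**Conclusion.** The point holds and is minor. The plan controls error across domains at Week 12 and not at Weeks 8 and 4, yet calls all three confirmatory. The worst-case chance of at least one false rejection is about 8–22% with five domains effective at Week 12 only (8–14% at the more plausible between-domain correlations) and about 6–9% with one. These figures assume 120 evaluable per arm, 0.5 SD where effective, and correlations that the documents do not give. They are limits for judging strong control and not forecasts.

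It would be wrong to conclude that the primary analysis is compromised. The Week 12 Holm family, the success rule and control under the global null are all sound.

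**What to change.** In Protocol 8.3 and SAP 5.4.1.2, keep the Week 12, 8, 4 order as a guide to interpretation and make these text changes:

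- Where earlier timepoints are said to be assessed for confirmatory evidence, write *interpreted as supportive evidence*.
- Replace the opening of the gate sentence with *Each domain's earlier timepoints will only be interpreted as supportive if*, leaving its Week 12 condition as it is.
- Add: *Week 8 and Week 4 p-values are non-adjusted, are not controlled for multiplicity across the five domains, and will not be presented as confirmatory.*
- In Protocol 8.3, state that the multiplicity adjustment across domains applies to Week 12 only.
- In Protocol 8.3.2, change the reference from Section 8.2 to 8.3.

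Holm at Week 12 is unchanged. The cost is that confirmatory status at Weeks 8 and 4 is given up. SAP Appendix 2 already records a change decided at the blind data review, so this edit would also have to be documented as made before unblinding. If that is no longer possible, the limitation should be stated in the report. If the sponsor wants confirmatory claims at the earlier visits, the level has to be split across domains, for example by a graphical procedure. That trades away some Week 12 power in individual domains; it is a separate decision for the sponsor and not part of this fix.
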